9.3 Statistical Analysis

9.3.1 Statistical analysis plan

SPSS version 26.0 software was used for statistical analysis. Baseline data were analyzed according to the full analysis set, and all efficacy indicators were analyzed according to the full analysis set and the per-protocol set; safety analysis was performed using the safety analysis set.

Descriptive statistics were used to analyze all data, including demographic data, baseline, various efficacy evaluation indicators, and all safety data. Measurement data were expressed as mean \pm standard deviation or median and upper and lower quartiles, and count data were expressed as frequency or percentage. Dropout was defined as any reason that caused the subject to fail to complete the follow-up required by the protocol. For exclusion, dropout cases were statistically described one by one. The anti-tumor efficacy of nimotuzumab was analyzed in the full analysis set and the per-protocol set.

9.3.2 Effectiveness Analysis

Kaplan-Meier curves were drawn to estimate the survival rate, median survival time, and hazard ratio.

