Study intervention	
1.Radiation Therapy
 
The prescription dose required that 95% PTV and PTV-nd receive 50-60 Gy /25-30 F , with a single dose range of 2.0 Gy/F, 5 days a week, external beam radiation to the chest .
 
2.Treatment
 
S-1: 40-60 mg/m² , po, D1, BID, 5 weeks;
 
Nimotuzumab 400 mg, iv, D1, week 1;
 
Nimotuzumab 200 mg, iv, D8, QW, Week 2-5.

Study duration	The estimated time from the start of the study to the completion of data analysis is 40 months
Visit duration	The planned enrollment period for this study is 12 months, and the time required for each subject to complete all visits are 24 months.

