9.1 Sample size estimation

This study is a single-arm, prospective, exploratory, single-center phase II clinical study. The sample size calculation was based on the primary study endpoint, namely, PFS assessed by the investigator.

The primary endpoint was the median PFS assessed by the investigator. Based on previous studies on radical radiotherapy for elderly esophageal cancer, the median PFS of elderly patients with locally advanced and inoperable esophageal squamous cell carcinoma after radical radiotherapy was 16 months. It was estimated that the median PFS of this study could reach 18.2 months. Using a one-sided test, $\alpha=0.05$, power=0.80, the sample size was calculated to be 41 cases. Considering the dropout rate of 20%, a total sample size of 52 subjects was required.

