10.1.2 Study suspension and termination

If there are sufficient reasonable reasons, this study may be temporarily suspended or terminated early. The party that suspends or terminates the study should notify the subjects and researchers in writing and record the reasons for the suspension or termination of the study. If the study is terminated or suspended early, the principal investigator (PI) should promptly notify the subjects and the Institutional Review Board (IRB) and provide the reasons for the termination or suspension of the study.

Circumstances that may require termination or suspension include, but are not limited to:

- Determination of unexpected, significant, or unacceptable risks to subjects;
- Demonstration of effectiveness provides justification for cessation;
- Insufficient compliance with protocol requirements;

- Data are incomplete and/or insufficient for evaluation;
- Determination that the primary endpoint had been met;
- Determine that the study is invalid.

The study may proceed only if issues related to safety, protocol compliance, and data quality are addressed.

11. References

[2] Rustgi, Anil K, and Hashem B El-Serag. "Esophageal carcinoma." The New England journal of medicine vol. 371,26 (2014): 2499-509.

[3] Domper Arnal, María José et al. "Esophageal cancer: Risk factors, screening and endoscopic treatment in Western and Eastern countries." World journal of gastroenterology vol. 21,26 (2015): 7933-43.

[4] Yu, Canqing et al. "Hot Tea Consumption and Its Interactions With Alcohol and Tobacco Use on the Risk for Esophageal Cancer: A Population-Based Cohort Study." Annals of internal medicine vol. 168,7 (2018): 489-497.

[6] Wang Lili, Wang Jian, Yu Bo, Liu Huilan, Hu Lijun, Zhou Juying. Analysis of toxic and side effects of radiotherapy and prognostic factors in elderly patients with esophageal cancer[J]. Chinese Journal of Oncology Prevention and Treatment, 2018, 25(23): 1638-1642.

[7] Jiang, Dongxian et al. "The prognostic value of EGFR overexpression and amplification in Esophageal squamous cell Carcinoma." BMC cancer vol. 15 377. 8 May. 2015.

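### Section 9.1 sizes the trial for a one-sided test of median PFS that section 9.3 does not contain, and that test would have about 14–20% power, not 80%

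*Protocol*

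**What the plan says.** Protocol section 9.1 takes 16 months as the median PFS after radical radiotherapy in earlier studies and then sets the target: "It was estimated that the median PFS of this study could reach 18.2 months". It specifies a one-sided test at alpha 0.05 and concludes: "power=0.80, the sample size was calculated to be 41 cases". Allowing for 20% dropout it arrives at 52; the synopsis in section 1.1 plans 50. Section 9.1 names no test statistic and no number of events. It also labels the trial: "This study is a single-arm, prospective, exploratory, single-center phase II clinical study".

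Section 9.3.1 states: "Descriptive statistics were used to analyze all data, including demographic data, baseline, various efficacy evaluation indicators, and all safety data". Section 9.3.2, on effectiveness, is a single sentence: "Kaplan-Meier curves were drawn to estimate the survival rate, median survival time, and hazard ratio". Section 9.3 mentions neither the 16-month reference nor a decision rule.

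On follow-up, section 1.1 gives 12 months of enrolment and says "the time required for each subject to complete all visits are 24 months", within a 40-month study.

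**The concern.** Sections 9.1 and 9.3 do not describe the same trial. The first is a hypothesis test with an error rate and power; the second is estimation without a comparison. If section 9.3 is followed as written, the alpha and power in 9.1 refer to nothing the trial does. If the test is added, the question is whether it has the power claimed. Without that power, a non-significant result would be likely even if 18.2 months were true, and readers would have been told of 80% power that never existed.

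The hazard ratio is a separate defect in the same sentence. Kaplan-Meier curves give survival probabilities and quantiles. A hazard ratio needs a second hazard, and this single-arm protocol names neither a comparator nor a reference hazard.

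**Working it through.** **Inputs.** From section 9.1: medians 16 and 18.2 months, one-sided alpha 0.05, power 0.80, n = 41, 20% dropout, total 52. From section 1.1: n = 50, 12 months of enrolment, 24 months of visits per patient, 40 months overall. Two assumptions are mine: PFS is exponential, and follow-up is either 24 months each or uniform over 24–36 months (common cut-off at month 36).

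**Step 1: the plan's own figures.** The dropout step reproduces: 41/(1 − 0.20) = 51.25, rounded up to 52. The 41 does not. For a one-sample test on the log hazard:

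events = (1.645 + 0.842)² / [ln(18.2/16)]² = 372.5, so 373.

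Other one-sample forms need 372–405 events. Even a one-sided alpha of 0.20 needs 171. For 41 patients to give 80% power against 18.2 months, the null median would have to be about 10.5–12.3 months. Against a null of 16, the alternative would have to be about 24–28 months. These ranges span follow-up patterns from 12 months' minimum up to an event in every patient.

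**Step 2: expected events if the true median is 18.2 months.** With 24 months each, P(event) = 1 − 2^(−24/18.2) = 0.599. With 24–36 months it averages 0.678.

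| n | 24 months each | 24–36 months |
|---|---|---|
| 41 | 24.6 | 27.8 |
| 50 | 30.0 | 33.9 |
| 52 | 31.2 | 35.3 |

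**Step 3: power.** In closed form, power = Φ(ln(18.2/16)·√D − 1.645) for D events:

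- D = 25: 0.158
- D = 35: 0.189
- D = 52 (an event in every patient): 0.237

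The one-sample log-rank test was simulated with 100,000 runs per setting, n = 41–52, both follow-up patterns. With variance E, power is 0.139–0.173 and type I error about 0.04. With variance (O+E)/2, power is 0.17–0.20 and type I error slightly above 0.05. If minimum follow-up were only 12 months, simulated power would be 12–17%. Kaplan-Meier tests at 12 or 16 months give 12–17%, and exact binomial tests of landmark PFS 9–16%.

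**Step 4: what an observed 18.2 months would show.** The 90% CI, which matches a one-sided 5% test, is 18.2·exp(±1.645/√D): 13.1–25.3 months at 25 events and 13.8–24.0 at 35. Both include 16. To exclude 16, the observed median would have to exceed 16·exp(1.645/√D), which is 22.2 months at 25 events and 21.1 at 35.

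**Step 5: precision if the trial is descriptive.** For a Kaplan-Meier median of 18.2 months, the SE on the log scale is 1/(ln2·√n), with no censoring before the median. For the landmark rates, SE = √[S(1 − S)/n].

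| Quantity | 95% CI, n = 41 | 95% CI, n = 50 |
|---|---|---|
| Median 18.2 months | 11.7–28.3 | 12.2–27.1 |
| 1-year PFS 63% | 49–78% | 50–77% |
| 2-year PFS 40% | 25–55% | 27–54% |

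**The case against.** The strongest reply is that only the protocol is at hand, and naming a test and its variance form is commonly left to an SAP. Section 9.3.1 applies description to all data without saying that nothing else will be done. That stands: a missing test name would not by itself be a finding. But no test an SAP could add, on the inputs fixed in section 9.1, comes near 80% power with 41–52 patients.

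Second, the trial calls itself exploratory, and no decision rule hangs on the test. A descriptive trial is legitimate, but the paragraph that uses the label also claims a one-sided test with 80% power. The label limits the severity and does not reconcile the two.

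Third, the hazard ratio is undefined rather than impossible, since an observed/expected ratio could be meant. Agreed; the protocol has to say so.

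Fourth, the event counts ignore dropout. With 20% loss by 24 months (an assumption), 52 patients would yield about 28–32 events and power of 17–18%, so the upper figures are slightly generous and the conclusion is unchanged.

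Finally, the upper confidence limits for the median lie beyond 24 months, but imaging continues until progression. In simulation the upper limit is reached in 27–35% of trials if follow-up stops at 24 months each, and in 78–86% with 24–36 months. Whether the median's interval is usable therefore depends on follow-up that the protocol leaves unclear, which is why landmark rates should accompany it.

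**Conclusion.** The concern holds. The analysis in section 9.3 does not contain the test that justifies the sample size in 9.1, and that test would have about 14–20% power with 41–52 patients, not 80%. The exact figure rests on exponential PFS and on 24 to 36 months of follow-up, because the protocol states neither a distribution nor an event count. The conclusion does not depend on those details: even an event in all 52 patients leaves power at 24%. The hazard ratio in 9.3.2 has no reference and cannot be obtained from the Kaplan-Meier curve. The data remain usable for estimation, so this should be corrected but does not undermine the trial as a descriptive study.

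**What to change.** Correct sections 9.1 and 9.3 together, in one of two ways.

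**(a) Keep the test.** Name one primary analysis in 9.3.2: a one-sample log-rank test of observed events against those expected at hazard ln2/16 per month, one-sided alpha 0.05, with its variance form. State in 9.3.1 that this analysis is not merely descriptive. Restate the power in 9.1 as about 14–20%, or resize. Keeping 80% power would take 373/0.678 = 550 to 373/0.599 = 622 patients at the same follow-up, or about 690–780 after dividing by 0.8 for dropout.

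**(b) Declare the trial descriptive.** Remove alpha and power from 9.1 and justify the sample size by the precision of the median and the 1- and 2-year PFS rates, using figures like those in the last table above. The trial then gives up a formal claim against 16 months. As an optional follow-on, two generic grounds for termination in section 10.1.2 could be aligned, since both presuppose a success criterion: "Determination that the primary endpoint had been met" and "Demonstration of effectiveness provides justification for cessation".

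In both cases, report the Kaplan-Meier median and the 1- and 2-year rates with confidence intervals. Delete the hazard ratio, or define it as observed over expected events against the 16-month reference; it would be about 16/18.2 = 0.88 if 18.2 months is true.

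Option (b) fits the exploratory label and the planned size. Without resizing, either option costs only wording and changes no treatment or visit.

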9.3.3 Security analysis

- 1)Describe the therapeutic exposure;
- 2)Statistics of adverse events, the incidence and severity of serious adverse events (NCI CTCAE 5.0), and the causal relationship with the trial drug;
- 3)The vital signs, laboratory test values, electrocardiograms and changes relative to baseline levels of the subjects at each follow-up point will be statistically analyzed descriptively, and data that deviate from the reference value range will also be statistically analyzed;
- 4)Concomitant medications and concomitant therapies will be categorized and counted.

10. Supporting documents and operational considerations

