6.1 Study intervention management

6.1.1 Description of study intervention

Intervention Name	Dosage form	Manufacturer	Specification	Administration route	Storage and stability
Nimotuzumab	Injection	Biotech Pharmaceutical Co., Ltd.	50mg/bottle (10ml)	Intravenous injection	This product should be stored and transported at 2°C-8°C and should not be frozen. The shelf life is 24 months. After dilution with normal

					saline, this product can remain stable for 12 hours at 2°C-8°C and 8 hours at room temperature. If stored for longer than the above time after dilution, it should not be used.
S-1	Capsule	Jiangsu Hengrui Medicine Co., Ltd./Qilu Pharmaceutical Co., Ltd.	20mg/capsule	Oral	Protect from light, seal tightly, and store at room temperature.

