6.1.2 Dosage and administration

S-1: 40-60 mg/m², po, D1, BID, 5 weeks;

Nimotuzumab 400 mg, iv, D1, week 1;

Nimotuzumab 200 mg, iv, D8, QW, Week 2-Week 5.

Radiation Therapy:

Intensity modulated radiation therapy (IMRT) technology is used to irradiate the involved field. The patient is placed in a supine position and fixed with the head, neck, shoulder or body membrane. The patient is simulated and positioned under CT. The CT image is transmitted to the treatment planning system. Combined with esophageal barium meal contrast, gastroscopy or ultrasound gastroscopy or PET-CT images, the esophageal tumor target volume (GTV) is outlined layer by layer on the enhanced CT image; the clinical target volume (CTV) is the GTV with an axial expansion of 0.6 to

0.8 cm and an upper and lower expansion of 2.0 to 3.0 cm; the planned target volume (PTV) is the CTV with an expansion of 0.5 to 0.8 cm. The metastatic lymph nodes are outlined as GTV-nd, and the GTV-nd with an expansion of 0.8 to 1.0 cm is PTV-nd. The prescription dose requires that 95% of PTV and PTV-nd receive 50 Gy /25 F , with a single dose range of 2.0 Gy/F. The target dose distribution and the dose of organs at risk are evaluated layer by layer on the cross section, and the dose-volume histogram (DVH) is combined to evaluate and optimize the treatment plan. The maximum spinal cord dose is <45 Gy, lung V20 <28%, V30 <20%, and the average lung dose Dmean \leq 15 Gy. After the treatment plan is confirmed, the dose is verified on the treatment machine, and the treatment plan is executed after it is accurate.

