8.2.3.2 Relevance to the study intervention

The clinician examining and evaluating the subjects must assess the relevance of all adverse events to the study intervention based on the timing and his/her clinical judgment. In clinical studies, the study intervention must always be a subject of suspicion.

Grading of relevance of study intervention:

- 1) Definitely related: There is clear evidence of a causal relationship and other possible factors can be ruled out. The clinical event (including abnormal laboratory test results) occurs in a reasonable time relationship with the administration of the study intervention and cannot be explained by concurrent illness, other drugs or chemicals. The response of withdrawing the study intervention (de-challenge) should be clinically reasonable. The event must be pharmacologically or phenomenologically clear, and if necessary, a qualified re-challenge procedure can be used;
- 2) Probably related: There is evidence of a causal relationship and the likelihood of other factors being influential is low. The clinical event (including laboratory abnormalities) occurred within a reasonable period of time after the study intervention was given and is unlikely to be attributed to concurrent illness, other drugs or chemicals, and is consistent with a clinically reasonable withdrawal (de-challenge) response. No re-challenge information is required to complete this definition;
- 3) Possibly related: There is some evidence of a causal relationship (e.g., the

event occurred within a reasonable period after administration of the trial drug). However, other factors may have contributed to the event (e.g., the subject's clinical condition, other concomitant events). Although an adverse event may be classified as "possibly related" soon after discovery, it can be recorded as requiring more information and then upgraded to "probably related" or "definitely related" depending on the circumstances;

- 4) Likely unrelated: The temporal relationship between the clinical event (including laboratory abnormalities) and the administration of the study intervention indicates that a causal relationship is unlikely (e.g., the event did not occur within a reasonable period after the administration of the study intervention), and other drugs, chemicals, or underlying diseases can provide a reasonable explanation (the subject's clinical condition, other concomitant treatments);

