8.2.5 Serious adverse event reporting

After receiving safety-related information from any source, researchers should immediately analyze and evaluate it, including its severity, relevance to the trial drug, etc. Suspected and unexpected serious adverse reactions should be promptly reported to the clinical trial institution and ethics committee.

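### Adverse event causality is graded against the study intervention, which includes radiotherapy, but is analysed and screened for reporting against an undefined trial drug

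*Protocol*

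**What the plan says.** Section 8.2.3.2 of the protocol sets the grading task: the examining clinician "must assess the relevance of all adverse events to the study intervention based on the timing and his/her clinical judgment". It gives one five-level scale, from definitely related to definitely unrelated, and describes no grading by treatment component.

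Radiotherapy belongs to the study intervention in two places. The study intervention row of the Summary lists it first, as "5 days a week, external beam radiation to the chest". Section 6.1.2, which sits under the study intervention chapter, describes it alongside the S-1 and nimotuzumab regimens: "Intensity modulated radiation therapy (IMRT) technology is used to irradiate the involved field".

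The later uses of the grade name something else. Section 8.2.5 asks for each safety report to be evaluated for its "relevance to the trial drug". Section 9.3.3, item 2, plans to summarise adverse events, serious adverse events "and the causal relationship with the trial drug". Section 8.2.4 says that the relationship to be collected is to the investigational product. Inside the scale itself, the example under level 3 (possibly related) is timed from the trial drug, while the other levels refer to the study intervention.

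**The concern.** The grade is collected against one object and used against another, and no rule converts the first into the second. Three components are given concurrently, and two of them are drugs. Radiation esophagitis is plainly related to the regimen, but need not be related to a drug. If the grades are tabulated as they stand under a trial drug label, radiotherapy toxicity is presented as drug toxicity. If clinicians grade with the drug in mind, radiotherapy toxicity may be left out. Different clinicians may also read the instruction differently within the same table.

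Two outputs are at stake: the descriptive causality summary in 9.3.3, and the relatedness judgement in 8.2.5 that helps decide which serious events are promptly reported as suspected unexpected reactions. The problem arises at collection. If one grade per event is recorded for the whole regimen, no later analysis plan can recover which component was suspected.

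**Working it through.** The protocol gives no figure on this point, so no arithmetic applies. The check sets the terms side by side and then follows some expected events through the scale.

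**Step 1: the object of causality, by section**

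| Protocol section | Purpose | Object named |
|---|---|---|
| 8.2.3.2, opening and levels 1, 2, 4, 5 | grading | study intervention |
| 8.2.3.2, level 3 example | grading | trial drug |
| 8.2.4 | item to collect for each event | investigational product |
| 8.2.5 | evaluation for serious-event reporting | trial drug |
| 9.3.3, item 2 | safety summary | trial drug |

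**Step 2: what the terms cover**

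- *Study intervention* includes radiotherapy in the Summary and in 6.1.2. The table under "6.1.1 Description of study intervention" lists only nimotuzumab and S-1, but its columns are dosage form, manufacturer, specification, route and storage. It is a product table, so nothing is inferred from the missing radiotherapy row.
- *Trial drug* is not defined. Section 9.3.1 speaks of the anti-tumor efficacy of nimotuzumab, which points to nimotuzumab alone. Section 6.3 refers to study drugs in the plural, which points to more than one product.
- *Investigational product* is not defined either.

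Three readings are therefore open: (A) the whole regimen, (B) nimotuzumab plus S-1, (C) nimotuzumab alone.

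**Step 3: expected events under each reading**

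The scale depends on alternative explanations. The upper levels require that other causes be excluded or unlikely. Level 3 allows that other factors contributed. Level 4 applies when something else reasonably explains the event, and level 5 when another documented cause is established.

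- *Radiation esophagitis.* Under A it is related, because radiotherapy is part of the object. Under B or C radiotherapy becomes the competing cause, and the grade can fall to any lower level.
- *Low neutrophil or white cell counts.* Section 2.3.1 lists these as common with nimotuzumab. Under A or B, S-1 is part of the object. Under C, S-1 becomes another drug that can explain the event and lower the grade.
- *Pneumonitis.* Section 2.3.1 includes lung inflammation among the serious reactions reported with nimotuzumab. Under B or C a clinician could still choose possibly related, or could attribute the event to radiotherapy.

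The same event can thus receive different grades depending only on the word the clinician follows.

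**Step 4: what depends on the grade**

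- The safety endpoint in the Summary and section 3 is AE/SAE incidence, with no causality condition, and 8.2.4 requires all events to be recorded whatever their cause. Neither depends on the grade.
- The causality part of 9.3.3, item 2, depends on it directly.
- Prompt reporting under 8.2.5 depends on it together with expectedness under 8.2.3.3.

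**The case against.** The strongest reply is that this is loose vocabulary with little consequence. The stated aim is the safety of nimotuzumab combined with chemoradiotherapy, so the regimen reading is natural throughout. The safety endpoint is all-cause, and no related-event rate serves as an endpoint, threshold or stopping rule. CRF layout and by-component tables are commonly left to the CRF or the analysis plan, neither of which is shown, and a separate grade per component may already exist there. Much of this stands: it limits what is affected and keeps the point away from the efficacy conclusions. It does not remove the contradiction, which lies between sections of the protocol itself.

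Four stronger readings are tempting and are not supported.

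- *That 6.1.1 removes radiotherapy from the intervention.* Its omission there follows from the product-table format.
- *That the trial's purpose of isolating nimotuzumab's toxicity is defeated.* The protocol states no such purpose, and a single arm could not achieve it however causality is coded.
- *That a fatal radiation pneumonitis would go unreported.* Under 8.2.2 the cause of death is recorded as a serious adverse event, and all events are tabulated. Only prompt reporting under 8.2.5 turns on relatedness, and expectedness also decides it. Section 8.2.3.2 also tells the clinician to keep the intervention under suspicion throughout. A definitely unrelated grade is a worst case.
- *That the related-event rate would move between about 6% and 100%.* A reader could derive this from the 16-patient elderly series in section 2.2: all had radiation esophagitis (16/16 = 100%) and one had a rash (1/16 = 6.25%). As described, that series reports no causality grades and was nimotuzumab plus radiotherapy without S-1. Assigning only the rash to the drug would be the reader's own attribution.

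**Conclusion.** The point holds as a contradiction in terms with a limited but real consequence. Grading is against an intervention that includes radiotherapy, while the descriptive causality summary and the relatedness judgement for serious-event reporting refer to an undefined trial drug. Radiotherapy-caused events may be counted or left out depending on the reading, and S-1-caused events too if trial drug means nimotuzumab alone. The direction and size of the effect in this trial cannot be estimated from the documents.

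The conclusion assumes that causality is collected as the protocol describes it, with no component split in the CRF. If such a split exists, only the wording needs correcting. The primary endpoint and the AE/SAE incidence endpoint stand as planned. The change is worth making because component attribution that is not recorded when the event is assessed cannot be derived later.

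**What to change.** 1. In 8.2.3.2, ask for a separate causality grade for nimotuzumab, for S-1 and for radiotherapy, each on the existing five-level scale, and reword the level 3 example to match.
2. Derive relation to any study treatment as the highest of the three grades.
3. In 8.2.5, use that derived flag as the relatedness criterion for serious-event reporting.
4. In 9.3.3, item 2, tabulate causality overall, using the derived flag, and by component.
5. In 8.2.4, replace the reference to the investigational product so that 8.2.3.2, 8.2.4, 8.2.5 and 9.3.3 all name the same objects.

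The table in 6.1.1 needs no change.

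The cost is up to two extra CRF fields per adverse event and aligned wording in four sections, with no added visits. The remaining weakness is that attribution by component stays a clinical judgement where toxicities overlap, such as low blood counts or lung inflammation. The by-component tables should be read with that in mind.
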